With advanced data extraction provided by xMSanalyzer and apLCMS, I will be able to also measure a spectrum of high and low abundance metabolites. We will utilize a well-established computational metabolomics workflow with rigorous standard operating procedures outlined in Fig. 7.¹²⁴ Data Selection and Annotation (Biostatistics and Bioinformatics Tools): HRM data will be processed using apLCMS with xMSanalyzer^{125,126}. Feature annotation will be performed using xMSannotator.¹²⁷ xMSannotator provides confidence scores for more than 2,000 metabolites, with more than 300 metabolites having confirmed identities and including most major pathways. The quality of data will be judged based on established rigorous criteria (e.g. coefficient of variation within replicates and QC samples, the percentage of missing values, the percentage of data exceeding detection limits of the machinery, batch-effects, and the percentage of outliers, etc.). Principal Component Analysis (PCA) will be used for batch-effect evaluation and ComBat¹²² will be used for batch- effect correction if necessary. Identifying expressed metabolites across different time points: we will use univariate and multivariate statistical methods, such as linear mixed effects models with post-hoc Tukey tests, LIMMA, and multilevel sparse Partial Least Squares Discriminant Analysis (msPLSDA).^{128,129} Multiple hypotheses testing correction will be performed using the Benjamini-Hochberg method.¹³⁰ Identifying putative biomarkers: we will use a consensus feature selection approach such that metabolic signatures identified by both univariate and multivariate approaches will be used for downstream analyses. K-fold and leave-one-out cross-validation using Support Vector Machine (SVM) will be performed to evaluate predictive accuracy of putative biomarkers. Two-way hierarchical clustering analysis will be performed to identify clusters of correlated metabolic features and to evaluate the ability of the discriminatory features to separate samples based on stress-hyperglycemia. Pathway enrichment analysis: Pathway analysis will be performed with pathway enrichment software for untargeted metabolomics data (Mummichog and MetabNet)^{131,132}. Where appropriate, additional chemical verification will be performed for significant metabolites of interest according to retention time and characteristic ion dissociation (MS/MS) patterns relative to authentic standards. Metabolome-wide association study (MWAS) of specific metabolites will be conducted (MetabNet) to facilitate detection of their related metabolic pathways and network structures in association with glucose levels (continuous) and stress-hyperglycemia as a discrete dichotomous variable.

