Extensive data from observational and prospective randomized controlled trials (RCT) in hospitalized patients have reported a strong association between stress hyperglycemia and poor clinical outcome, such as increased mortality, morbidity, hospital length of stay (LOS), infections and overall complications. This relationship is well established, and a dose response is consistently observed. This association is more robust among non-diabetic subjects compared to patients with diabetes or normoglycemia. Millions of cardiac surgeries are conducted globally and there is an urgent need to understand the mechanisms that lead to hyperglycemia during stress conditions and strategies to improve meaningful clinical outcomes. Cardiac surgery, in particular coronary artery bypass graft (CABG), is a unique human model for the study of metabolic changes during surgical stress. In our own study we have shown a reduction in a composite score of complications in subjects without diabetes undergoing CABG surgery randomized to a more intensive glycemic target. Our current approach to treat hyperglycemia, however, is reactive, it demands high resource utilization (staff needs to monitor glucose levels hourly and adjust intravenous insulin doses frequently), and if not done carefully is associated with a very high risk of iatrogenic hypoglycemia (up to 35%), which also carries a high risk of complications. This novel, exploratory study will characterize metabolic signatures during stress hyperglycemia, integrate findings with clinically meaningful biomarkers, and provide preliminary estimates of the effect of a long acting GLP-1 receptor agonist on the prevention of stress hyperglycemia.

- Study Population Characteristics:** Clinically stable adults scheduled to undergo coronary artery bypass graft surgery (CABG) will be studied. We expect that a total of 90 subjects will complete this project. A proportion of patients will be derived from the placebo arm of the randomized trial. This design will allow efficient recruitment from our cohort of CABG patients to allow substantial savings in cost and time. For Aim 1 a total of 50 patients will be included. In Aim 2 patients will be randomly assigned to dulaglutide (N=30) or placebo (N=30) one to three days before surgery. For both aims subjects must meet the inclusion and exclusion criteria listed below:

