- **Group Assignment / Case Definition:** Clinically stable adults scheduled to undergo coronary artery bypass graft surgery (CABG) will be studied. For logistic purposes recruitment will favor assignment to the clinical trial in the beginning of the award period (Aim 2, N=60). We expect a total of 30 subjects will be randomized to each group (dulaglutide or placebo). Thirty patients assigned to placebo in the clinical trial will contribute to the cohort of patients to be included in the nested case-control study. Cases and controls will be categorized prospectively on arrival to the surgical intensive care unit (SICU) (Cases are defined as BG >140mg/dL on ICU arrival). To further avoid selection bias, 25 age-matched controls will be selected for comparison. Once the number of cases is completed, additional potential controls will be selected (+/- 3 years) based on the characteristics of the population of cases. If additional patients develop stress hyperglycemia no further samples will be collected. This design will allow for efficient recruitment from our cohort of CABG patients to allow substantial savings in cost and time.
- **Research Sites:** All human subjects' research will be performed on the campus of Emory University, Atlanta, GA, and at Emory Affiliated Hospitals. Sites include Clinical Research Units (CTSA) where samples will be stored. Data collected are kept confidential and protected as per HIPAA regulations. Data collected at each facility will be shared only with the study team.

E.1.2. Study Endpoints and Sources of Materials:

- In the case control study (Aim 1) we will compare metabolic and hormonal profiles between subjects that develop stress hyperglycemia compared to controls. In an open-label format (Aim 2) we will assess whether exposure to dulaglutide is associated with a reduction in the frequency of stress hyperglycemia compared to placebo (primary endpoint). Prospectively, we will assess the association of candidate metabolites and metabolic pathways with the onset of stress hyperglycemia. Potential mechanisms underlying these associations will be explored by examining whether the associations of exposure to dulaglutide and prevention/improvement of glycemic control can be explained by changes in metabolic pathways (and key metabolites within these pathways) measured in plasma that occur between 3 days prior to surgery (baseline) and during the perioperative period. Addressing these research questions

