will be possible using innovative ultra-high resolution mass spectrometry (HRMS) with liquid chromatography (LC) and gas chromatography (GC) and advanced data extraction algorithms. LC-HRMS will also measure >2000 metabolomic intermediates in plasma at the time of surgery and at follow-up, providing coverage of >85% of human metabolic pathways. ***The overall hypotheses are that candidate metabolites such as: ceramides, acylcarnitines, and branched-chain amino acids (BCAAs) are associated with incident stress hyperglycemia, and that hyperglycemia leads to changes in path-specific biomarkers related to CV risk. In addition, exposure to an agent associated with low risk of hypoglycemia can positively affect the trajectory of metabolic changes during acute surgical stress.***

Baseline measurements: Samples will be collected up to seven days prior to scheduled CABG surgery. Blood samples will be processed by the CRN Laboratory and stored at -80°C until ready for batch analysis. Fasting plasma metabolomics analysis will be performed using high-resolution metabolomics (HRM) methods established in Co-mentor [name]' laboratory. Samples for measurement of biomarkers, glucose, cortisol, glucagon, insulin and c-peptide will also be collected. Indexes of insulin sensitivity/insulin resistance: will be derived from glucose, insulin and c-peptide values. Indexes of insulin secretion: pancreatic β-cell insulin secretion capacity will be assessed with HOMA-B.

Sources of materials: Research material will include medical history, demographic information, and complications obtained both from subjects, medical record, and study blood samples.

Data collected: Data to be collected is detailed in **Table 1** below, along with the source of the data. Baseline and daily information will be entered by [name] or a study coordinator into data collection paper forms and into an electronic database (REDCap) provided by the Emory Research Information Technology Department.

Table. Data to be collected and source

Data Item	Source
-Vitals (e.g. blood pressure, pulse, temperature)	Medical Exam
-Height, weight, BMI	Manual stadiometer and digital scale
-Demographic Information (e.g. age, race)	Self-report and medical records
-Medical history (e.g., comorbidities, surgeries)	Self-report and medical records
-Social history (e.g., education, smoking, alcohol use)	Self-report and medical records
-Indexes of insulin secretion, resistance and sensitivity	serial blood draws

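### Aim 1 adds controls after the case quota has filled and stops sampling later cases, with no matching, batching or adjustment for enrolment date, storage time or recruitment source

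*Combined protocol and SAP*

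**What the plan says.** The combined protocol and SAP sets the Aim 1 size in E.1.1: "For Aim 1 a total of 50 patients will be included". Under Group Assignment / Case Definition it adds that "25 age-matched controls will be selected for comparison", which leaves 25 cases by subtraction. The case rule is "Cases are defined as BG >140mg/dL on ICU arrival". Patients are classed prospectively at that moment.

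The same paragraph gives the selection rule in two halves. For controls: "Once the number of cases is completed, additional potential controls will be selected", within 3 years of age and guided by the characteristics of the case population. For cases: "If additional patients develop stress hyperglycemia no further samples will be collected". It also says that "recruitment will favor assignment to the clinical trial in the beginning of the award period", and that the 30 placebo patients feed the case-control study.

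Baseline samples are "stored at -80°C until ready for batch analysis" (E.1.2). The timeline in E.1.9 marks Aim 1 recruitment in years 1 to 4 and laboratory assays in years 4 and 5.

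On analysis, D1 Aim 1.1 accounts for age matching and names gender and smoking as adjustments. D1 Aim 1.2, for the untargeted data, says "Principal Component Analysis (PCA) will be used for batch-effect evaluation", with ComBat correction if needed. No section matches, stratifies or adjusts for enrolment date, storage time or trial versus non-trial source, and none says how cases and controls are spread over assay batches.

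**The concern.** If the case quota fills first, the last stretch of accrual yields controls only. Provided that the assays are run together at the end, those controls have been frozen for less time. They also had surgery in a later period of care and are more likely to be non-trial patients who received no placebo injection. Case status then partly tracks calendar time and source.

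A metabolite or biomarker that changes with storage or with surgical practice would then differ between cases and controls without any link to glucose. The untargeted screen covers more than 2,000 features, so it is well placed to pick up such differences. Benjamini-Hochberg correction controls chance findings and does not remove bias. The Aim 1 pitfalls paragraph also allows features with raw p<0.05 to go forward to pathway analysis when none passes the false-discovery threshold. If assay batches follow enrolment order, batch itself becomes partly confounded with case status.

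**Working it through.** **The plan's own figure.** E.1.9 calls N=50 more than adequate for an effect size above 1, alpha 0.05 and power 0.80 with a Wilcoxon test. For a two-sided test, n per group = 2 × (1.96 + 0.84)² / 1² = 15.7, so 16. Dividing by the Wilcoxon efficiency of 0.955 gives 17, and by its lower bound of 0.864 gives 19, so 34 to 38 patients in total. With 25 per group, power is about 0.91 to 0.94. The sample-size statement holds at unadjusted alpha; the question is bias.

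**Case rate.** The rate on ICU arrival is not given. The documents give any-time rates: about 60-80% (Specific Aims), about 60% (section A), at least half (D2 Rationale) and about 50-60% of placebo patients (E.1.3). They serve here as a proxy. In the same patients the arrival rate cannot exceed the any-time rate.

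**Expected late controls.** With case probability p, 25 cases are reached after 25/p patients on average, by when 25(1-p)/p controls have accrued. Late controls ≈ 25 - 25(1-p)/p:

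- p = 0.5: 25 - 25.0 = 0
- p = 0.6: 25 - 16.7 = 8.3
- p = 0.7: 25 - 10.7 = 14.3
- p = 0.8: 25 - 6.25 = 18.75

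**Simulation.** Patients arrive in sequence, the first 25 cases and first 25 controls are taken, and age matching is not modelled (20,000 runs). Accrual is spread evenly over 3.5 years, an assumption within the timeline's years 1 to 4. Drift is linear with no true case effect, and 0.2 and 0.3 SD per year are assumptions. Error is for an unadjusted two-sample t-test at nominal 5%. The last column is power for a 1 SD effect after adding enrolment date to a linear model.

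| Case rate | Late controls of 25 | Late share | Mean lag of controls (years) | Error, 0.2 SD/yr | Error, 0.3 SD/yr | Power with date term |
|---|---|---|---|---|---|---|
| 50% | 2.8 | 11% | 0.0 | 6% | 7% | 0.92 |
| 60% | 8.5 | 34% | 0.6 | 7-8% | 10% | 0.88 |
| 70% | 14.3 | 57% | 1.0 | 11% | 18% | 0.82 |
| 80% | 18.8 | 75% | 1.35 | 15% | 28% | 0.72 |

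A Wilcoxon test gives slightly lower error. At 45% and 40% the mean lag is about -0.3 and -0.6 years: controls usually fill first and the imbalance reverses. Without the date term, t-test power is about 0.93. With it, the error returns to about 5% at every rate.

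**Recruitment source.** Suppose the 30 placebo patients are the first 30 in Aim 1 (assumption). At 60% they supply 30 × 0.6 = 18 cases and 12 controls, so the placebo share is 18/25 = 72% of cases and 12/25 = 48% of controls. At 70% it is 21/25 = 84% and 9/25 = 36%. This imbalance needs no drift assumption.

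**Concurrent controls only.** Restricting to controls enrolled before the last sampled case gives power of about 0.90, 0.82, 0.70 and 0.49 at 50%, 60%, 70% and 80%.

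**The case against.** A reader might infer that the controls as a group come from a later period. The documents do not support that. Patients are classed prospectively, so controls accrue beside cases until the quota fills; at a 60% rate about two thirds are concurrent.

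A reader might also infer that the plan expects most patients to be cases. Its rates are for hyperglycemia at any time, while a case is defined on arrival. The 70% and 80% rows need an arrival rate above the plan's own any-episode range for placebo patients, and at 50% the mean lag is nil.

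The harm depends on a drift that the documents do not quantify, and at 0.2 SD per year and 60% the excess error is small for exploratory work. There is partial cover too. Serial samples allow within-patient change, which largely cancels an additive storage shift, and ComBat addresses assay batch. Dates of operation are collected (E.1.2 data table), so an adjusted analysis remains possible later.

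All of this stands, and it limits the size of the point. It does not remove it. Aim 1.1 also makes cross-sectional comparisons, and the pitfalls paragraph considers whether presurgical biomarkers predict hyperglycemia; neither benefits from within-patient change. Batch correction is conditional, covers only the untargeted data, and does not address storage time or era. No adjusted analysis is prespecified.

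**Conclusion.** The point holds for the controls added after the case quota fills. If more than half of patients are cases on arrival, those controls differ from cases in enrolment date, storage time and probably source, and no planned analysis deals with this. The late share runs from about 11% at a 50% rate to 75% at 80%. At 60% the excess error is modest under the assumed drifts; at 70% it is material.

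The size rests on three assumptions: any-time rates as a proxy for the arrival rate, even accrual over 3.5 years, and the drift itself. Age matching was left out. Section C.2 reports older age in patients with repeated hyperglycemia (67.0 against 59.1 years), so some early controls might not qualify, which would raise the late share.

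The documents do not show that any Aim 1 result would be false, nor do they fix the direction of the imbalance. What they show is a selection rule that can tie case status to calendar time, and an inexpensive safeguard that is missing.

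**What to change.** 1. In D1 Aim 1.2, and wherever that assay workflow is repeated, place cases and controls in balanced numbers in every assay batch, with random run order. Keep each patient's serial samples in one batch. If ComBat is used, keep case status in its model. Apply the same balance to the targeted assays.
2. In the D1 Aim 1.1 and 1.2 analyses, prespecify an adjusted comparison with operation or enrolment date (standing for storage time) and recruitment source (placebo arm or Aim 1 only). Add a sensitivity analysis limited to controls enrolled before the last sampled case.
3. In E.1.1, where feasible, spread case sampling over the accrual period, for example with a yearly cap on cases.

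Strict pairing on age and a narrow date window is not advised. At 60%, with an assumed age SD of about 9 years, a 6-month window cuts the attainable pairs from about 23 to about 17, so 25 pairs would need more recruits.

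The cost is wording, a run list and some power. Because date is correlated with case status, the date term reduces power as tabulated, to below the planned 0.80 if the case rate is 80%; adding source reduces it further. The concurrent-control analysis loses more and should be read as supportive. This loss is a reason to spread case sampling during accrual and not rely on adjustment alone.

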Rationale: At least half of non-DM patients undergoing cardiac surgery develop stress hyperglycemia,^{8,9,72,135} shown to be an independent risk factor of morbidity and mortality.^{10,12,14-16} To maximize exposure to subjects at high risk of stress hyperglycemia, we will enroll obese individuals older than 50 years of age. Most patients with stress-hyperglycemia require insulin infusion in the ICU and about half continue to receive subcutaneous insulin after transition to regular wards.^{24,136} GLP1 treatment has been shown to improve glycemic control similar to insulin administration in critically ill patients,⁸⁸⁻⁹⁰ CABG surgery,⁹² and in mixed ICU populations.⁹³ Dulaglutide is effective in improving glycemic control in patients with DM,¹⁰⁰⁻¹⁰² with lower rate of side effects compared to other long acting GLP-1-RA.¹⁰⁵ Phase 1 pharmacodynamics analysis in non-DM participants demonstrated median maximum plasma concentrations of dulaglutide between 24-48 hours after single-dose administration¹⁰³ with a dose-dependent rise in insulin secretion and progressive reduction in glucose concentration.¹⁰³ The rapid onset and sustained action, safety and efficacy with low-rate of hypoglycemia,^{102,137} indicate that dulaglutide is an ideal agent for the prevention of stress-hyperglycemia.

Study Design: This randomized, placebo controlled study will include 60 obese subjects with ages between 40-80 years of age without a history of diabetes [BG ≤ 125 mg/dl and HbA1c $< 6.5\%$] undergoing CABG surgery. Due to the study design (i.e. need of surgical care), there will be no run-in period. Women in childbearing potential will have urine β -HCG measured before participating in the study.

Study population:

Inclusion criteria: Males or females between the ages of 40 and 80 years and BMI $\geq 25\text{kg/m}^2$ undergoing elective CABG surgery. No previous history of diabetes or hyperglycemia.

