Inform consent and randomization: Patients will be consented during the preoperative evaluation on admission at least 24-72 hours prior to scheduled surgery. The investigators or study coordinators will review and explain the contents of the informed consent document to the eligible patient. Additional details are outlined in the Human Subjects section.

Study Sites: This pilot study will be conducted at Emory University Hospital, Emory Midtown Hospital, and Grady Memorial Hospital, Atlanta.

ICU Stay: Study patients who develop stress-hyperglycemia ($BG > 140$ mg/dl) in the ICU will be started on intravenous CII adjusted to maintain a BG target between 100-140 mg/dl following a standard hospital protocol.

Transition from ICU to Regular Floor: Patients with fasting and/or premeal $BG > 140$ mg/dl will receive coverage with sliding scale insulin (supplements), those with 2 consecutive $BG > 180$ mg/dl, or average daily $BG > 180$ mg/dl will be started on rescue therapy with SC basal insulin (glargine or levemir) once daily.¹¹¹

Rescue Therapy with Basal Insulin in Non-ICU Settings¹¹¹:

- BG between 140-200 mg/dl= start basal insulin at 0.1 units per kg weight per day.
- BG between 201-400 mg/dl= start basal insulin at 0.2 units per kg weight per day.
- Basal insulin will be given once daily, at the same time of the day.

Insulin adjustment and supplemental (correction) insulin: we will use a standard insulin treatment protocol.^{4,86}

Investigational drugs:

- Dulaglutide injection: 0.75 mg/0.5 mL solution in a single-dose pen will be provided to patients
- Saline injection/0.5 mL pre-drawn solution, a tuberculin syringe will be provided to patients
- A research pharmacist at the site-specific Clinical Research Network Unit will provide dulaglutide and saline. Patients will be instructed on self-injection technique.

Withdrawal Criteria (please see additional details in Human Subjects and DSMP sections):

- The subject may withdraw at any time during the study by primary care provider or research team.
- The subject may be withdrawn at the investigator's discretion due to a safety concern or for contravention to the inclusion and/or exclusion criteria.
- Subject diagnosed with acute pancreatitis by clinical and/or radiographic criteria.

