Analysis: The primary endpoint of Aim 2 is the frequency of stress-hyperglycemia ($BG > 140$ mg/dl) requiring insulin therapy during the postoperative period (Aim 2.1). We will use two-sided Chi-square test or Fisher's exact test for the primary outcome. In Aim 2.2 we will compare the difference in mean BG upon ICU arrival and the frequency of rescue therapy with SC insulin after transition to regular floor. We will also explore differences in complications between groups. Secondary outcomes of interest can be a binary outcome (e.g. whether CII is needed in ICU), or a count outcome (e.g. number of perioperative complications), or a continuous outcome (e.g. mean ICU BG concentration). We will adopt the same strategy proposed for the primary outcome to analyze any binary secondary outcomes. For secondary outcomes measured as counts, we plan to use nonparametric tests such as Krustal-Wallis tests. Univariate Poisson regression (or Negative Binomial regression) will be performed to estimate the marginal treatment effect. In addition, we will also conduct multivariate Poisson regression (or Negative Binomial regression) to assess the outcome differences between the two study groups with potential confounders considered. For secondary endpoints that produce continuous outcomes, we will use two-sample t-tests or nonparametric Wilcoxon tests to compare study groups.

Transformations will be applied if normality violation is detected.

Aim 2.3. To compare changes in metabolites and biomarkers in response to dulaglutide or placebo (measured in Aims 1.1 and 1.2), as well as beta-cell function and insulin resistance estimates.

Methods: Biomarkers and assessment of candidate metabolites will follow the same procedures as specified in Aim 1. Surrogates of beta cell function and insulin resistance will be derived from glucose, insulin, and c-peptide measurements acquired during the perioperative period.

[figure not shown]

Figure 8. Treatment groups in Aim 2. Patients will be assigned to receive dulaglutide or placebo 1-3 days before surgery.

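### Aim 2 is open-label, and its Analysis paragraph adds a need for insulin to a primary endpoint defined on glucose alone, so a treatment action by staff who may know the arm enters the primary result

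*Combined protocol and SAP*

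**What the plan says.** **Design.** Section D2 (Study Design) states: "This randomized, placebo controlled study will include 60 obese subjects". Section E.1.2 states: "In an open-label format (Aim 2) we will assess whether exposure to dulaglutide is associated with a reduction in the frequency of stress hyperglycemia".

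**Products.** D2 (Investigational drugs) lists "Dulaglutide injection: 0.75 mg/0.5 mL solution in a single-dose pen will be provided to patients" and "Saline injection/0.5 mL pre-drawn solution, a tuberculin syringe will be provided to patients". Patients are taught to inject themselves.

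**Masking.** No section describes keeping patients, ICU or ward staff, outcome recorders or the laboratory unaware of the arm. The data and safety monitoring plan is a separate document that I have not seen.

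**Primary endpoint.** D2, Aim 2.1, defines it as any hospital glucose above 140 mg/dl after CABG, with no mention of insulin. E.1.2 likewise speaks only of the frequency of stress hyperglycemia. The D2 Analysis paragraph narrows it to hyperglycemia above the same threshold "requiring insulin therapy during the postoperative period (Aim 2.1". The test is a two-sided chi-square or Fisher's exact test.

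**Insulin triggers.** In D2, ICU patients above 140 mg/dl are to start continuous insulin infusion (CII) under a standard hospital protocol. On the floor, fasting or premeal values above 140 mg/dl lead to sliding-scale insulin. E.1.3 and E.1.4 say hyperglycemia is treated by each hospital's standard protocols, and E.1.3 says this applies to both groups.

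**Glucose testing.** E.1.2 (Clinical Management Guidelines) sets testing every 1-2 hours during CII, and before meals and at bedtime on the ward. It gives no ICU interval before CII starts.

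**The concern.** Whether a laboratory or bedside meter reads above 140 mg/dl depends little on who knows the arm. Whether the patient then receives insulin is an action by the care team. When the endpoint requires both, and the team may know the arm, a difference between arms in giving insulin becomes a difference in the primary endpoint even if glucose is the same. The likely direction is toward dulaglutide: staff who believe the patient already has a glucose-lowering drug on board may hold back.

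The trial's purpose is to supply preliminary estimates for later randomized trials, so a bias here would carry forward into their design. There is also a reporting issue. The two primary endpoint definitions can give different counts, and the document does not say which one governs.

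**Working it through.** The plan gives no figure on this point, so there is none to reproduce. The check has two parts.

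**1. How far apart are the two definitions?**

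- In the ICU, the threshold that defines the event is also the threshold that starts insulin. If the rule is always followed, the definitions coincide there.
- On the ward, the stated sliding-scale trigger is a fasting or premeal value, but glucose is also measured at bedtime. A bedtime value above 140 mg/dl is an event under Aim 2.1 without being a stated sliding-scale trigger. The definitions are therefore close but not identical, even with full adherence.
- To drop out of the Analysis version, a patient must have every reading above 140 mg/dl go untreated for the whole postoperative stay. One treated reading makes the patient an event.

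**2. What would a treatment gap do to the test?**

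Inputs:

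- n = 30 per arm (E.1.1).
- True proportion h with glucose above 140 mg/dl, equal in both arms: 55%, the midpoint of the 50-60% expected on placebo (E.1.3), with 50% and 60% as the range.
- q = probability that a dulaglutide patient above 140 mg/dl receives insulin, relative to a placebo patient at the same glucose. The document gives no value. I assume 1, 0.9, 0.8 and 0.7, with every placebo patient above the threshold treated.

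Event probability as analysed: placebo p_P = h; dulaglutide p_D = h × q. At h = 0.55, p_D = 0.550, 0.495, 0.440 and 0.385.

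False-positive rate = Σₐ Σ_b Bin(a; 30, p_P) × Bin(b; 30, p_D) × 1{test significant at two-sided 0.05}, summed over all a, b from 0 to 30. For chi-square without continuity correction, the table is significant when

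|a − b|/30 ÷ √(2·p̄(1 − p̄)/30) > 1.96, with p̄ = (a + b)/60.

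Results (chi-square / Fisher):

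| q | h = 50% | h = 55% | h = 60% |
|---|---|---|---|
| 1 (no gap) | 5.2% / 2.7% | 5.1% / 2.7% | 4.9% / 2.6% |
| 0.9 | 6.9% / 3.9% | 7.3% / 4.2% | 7.6% / 4.3% |
| 0.8 | 12.3% / 7.7% | 14.0% / 8.9% | 15.7% / 10.1% |
| 0.7 | 21.7% / 14.8% | 25.4% / 17.7% | 29.3% / 20.9% |

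At h = 55% and q = 0.8, 13.7 of the 14.0 percentage points favour dulaglutide. With q = 0.95, chi-square gives only 5.7%.

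**With the Aim 2.1 definition,** q does not enter: both arms have event probability h, and the rates are those in the first row. This calculation does not cover unequal glucose testing, which could affect either definition.

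**The case against.** **Insulin is protocol-driven.** The written triggers use the same threshold as the event and apply to both arms. If they are followed, there is little room for discretion, and a patient is lost as an event only if every high reading goes untreated. This stands and is the main limit on the concern. A reader might infer that the primary result turns on a free staff decision, or that bias has been demonstrated. The documents support neither.

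**The glucose-only definition is already in the plan.** This also stands. The change is to make the Analysis paragraph agree with Aim 2.1, not to create a new endpoint.

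**Placebo controlled is not a claim of blinding.** Agreed. The term names the comparator, and E.1.2 discloses the open-label format. A reader might infer that the plan contradicts itself or promises masking; it does neither. A reader who sees only D2 could still assume masking, so the wording deserves clarifying.

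**The treatment gaps are assumed, and Fisher's test is milder.** Both are correct. At a 10% gap Fisher's test stays below 5%.

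**Other outcomes are partly protected.** Kidney injury, pneumonia and infarction have stated criteria, and tubes carry subject codes and are analysed in batches. The laboratory may therefore already be largely unaware of the arm.

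**Masking the care team is not free.** A reader might infer that it could be done at no cost because dosing precedes surgery. The documents do not show this. Patients know their device and can reveal it. The same investigators or coordinators may consent patients and record outcomes. The plan itself warns that insulin with this drug class may raise the risk of hypoglycemia, so treating clinicians need access to the allocation.

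**Conclusion.** The point holds in a limited form. The open-label format, the distinguishable products, the absence of any described masking and the extra insulin condition in the Analysis paragraph are all in the text. Together they leave a route by which knowledge of the arm can affect the primary result.

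The size is unknown. It depends on how far insulin would be given differently at the same glucose, for which the document has no data. With full adherence to the triggers in both arms, the effect of arm knowledge on insulin use would be close to nil. Under an assumed 20% gap, the false-positive rate would be about 12-16% with chi-square and 8-10% with Fisher's test, at true rates of 50-60% and 30 per arm.

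This is worth correcting because the remedy for the endpoint is a change of wording. It is not a fatal flaw in an exploratory study.

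**What to change.** 1. In the D2 Analysis paragraph, analyse the primary endpoint on recorded glucose above 140 mg/dl as Aim 2.1 defines it. Report insulin use as a secondary outcome. Cost: one sentence.
2. Describe Aim 2 in every section as open-label and saline-controlled. Cost: wording only.
3. State who knows the allocation. Where existing staffing allows, do not routinely disclose it to those recording glucose and complications or to the laboratory, and keep disclosure to treating clinicians always available for safety. Cost: low but not zero, since it may mean separating tasks now done by the same people. Masking will be partial because patients know their device.
4. Report the number of glucose readings per patient by arm, separately for the ICU before CII. Scoring on glucose alone does not remove unequal testing there, and this report would show whether it occurred. Cost: one table from data already collected.
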